3.1. Study Population

This intervention is offered to significant caregivers of a child between the ages of 3 and 18 who have questions about the support a child needs when confronted with a parent's cancer. In this study, the term "significant caregiver" refers to any person who provides significant practical, educational and emotional care to the child.

In order to respond to the heterogeneity of family and medical situations, each significant caregiver may decide to participate in the intervention alone or accompanied by a relative involved in the child's support.

The inclusion criteria for each participant are as follows:

- Participants must be of legal age (at least 18 years old);
- Participants must not have an acute psychiatric or neurological disorder that does not allow them to participate to the study and the intervention;
- Participants must have a sufficient command of French (speaking, writing and reading).

Participants cannot be included if:

- The child's parent with cancer is in a pre-terminal or terminal phase;
- The child's parent with cancer has died.

The sample size was calculated a priori to detect differences in the evolution of the two groups ("control" condition and "experimental" condition) between T1 and T2. A pilot study suggests a minimum expected effect size of 0.8 (effect size) if the GC remains stable. Under this double assumption, an overall population of 68 subjects (34 subjects in each group) will be required to achieve a level of significance (p) of 5% with a statistical power of 90%.

However, taking into account possible dropouts, the total recruitment sample should be 80 participants.

Regarding recruitment, as soon as a patient is identified by the team as having a child between 3 and 18 years of age, he or she is contacted to suggest the project. Information to identify and contact patients is taken from medical records. One study found that following or having recently followed chemotherapy or radiation therapy was associated with a higher level of

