parental competence (Moore, 2015). In this way, a more systematic recruitment will be organised within the Jules Bordet Institute at the day hospital and in radiotherapy in agreement with the department heads. In addition, in order to facilitate families' access to the project, the study is being disseminated to front-line carers (doctors, nurses, psychologists, social workers, NOC, etc.) within the Jules Bordet Institute, Erasmus Hospital and also in other hospitals via the distribution of information sheets and oral presentations.

3.2. Description of the study.

This is a randomized longitudinal controlled study conducted at the Jules Bordet Institute site and at Erasmus Hospital (Figure 1). This study evaluates the effectiveness of a psychological intervention focused on helping children in the oncology context. Significant caregivers may participate alone or in dyads at the intervention. At the time of recruitment (T0), after checking the eligibility criteria, participants receive all the information associated with the study. As a first step, they are offered the opportunity to perform the dyad intervention. If this is not possible, participants have the opportunity to participate in an individual way. After this step of presenting the information, they sign a consent form for inclusion in the study. As soon as they are included, the participants (in dyads or individually) have a first evaluation time (T1) consisting of the completion of questionnaires and a semi-directive interview.

[figure not shown]
At the end of T1, all participants (experimental condition and control condition) receive an information booklet entitled "How to talk with the child about a parental cancer? A practical booklet on communication. "[23] which contains parental information and recommendations associated with supporting a child facing a parent's cancer.

After T1, each participant is directly randomly assigned to either the experimental or control condition. Randomization is done after the first evaluation so that evaluators and participants are not aware of the distribution at T1.

After receiving the information booklet, participants randomized to the experimental condition receive a brief parental support intervention consisting of four sessions. Fifteen days after the end of the intervention, these participants have a second evaluation (T2), again consisting of the completion of questionnaires and a semi-directive interview.

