This is a brief four-session parental support psychological intervention that can be done individually or in a dyad. The first session is dedicated to a global assessment of the medical and family situation, communication with the child, as well as to an identification and reinforcement of the participant's parental skills. The second session suggests to the participant to identify the reactions and needs of children in the context of the disease and based on concrete examples. A construction work of what can influence perception is carried out. The last two sessions are devoted to the participant's specific questions about communicating with his or her children in the context of the disease.

In general, emotional regulation techniques specific to parenthood are worked on during the session and reinforced by the transmission of a relaxation booklet. Parental competence is systematically supported and strengthened. The content does not change whether one is in a dyadic or individual intervention except that dyadic interactions and support are enhanced.

Our workers are trained in the management of families through their clinical practice within the activities of "Bordet'N Family". In order to increase the fidelity of intervention replication, future practitioners will also benefit from a training process that involves three stages: general theoretical training in intervention, practical training specific to the intervention and

supervisions scheduled after each session with an experienced psychologist. In addition, the workers are supervised by the study coordinator ([name]).

A quality control of the intervention is set up by an audio and video recording of the interventions. These records are regularly analyzed using an analysis grid created from the intervention manual to verify the standardization of the intervention.

3.4. Evaluation procedure and questionnaires.

This study includes 2 evaluation periods, T1 and T2, consisting of the completion of questionnaires and a semi-directive individual interview. The evaluation procedure includes a research interview which is structured in three parts. The entire research interview lasts approximately 1h30.

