Before evaluating the effectiveness of the parental support intervention, the data will be examined to verify sample distributions and outliers. In addition, control analyses will be carried out to compare participants of experimental conditions and controls during T1 and to compare participants who performed T1 and T2 and those who dropped out (T1 completed). A comparative analysis between the group that performed the dyad intervention and the group that performed the intervention individually will be conducted in order to identify any differences in profile. An analysis using a mixed linear model including random effects will be used to compare the evolution of participants from the experimental condition to the control condition and consequently test the effectiveness of the intervention. This analysis will be done separately for participants who performed the intervention individually and those who did it in dyads. As for the content of the semi-directive interviews, a content analysis will be carried out.

4. Ethical and regulatory aspects.

This study does not present any risk to the physical health of the participants. Only questionnaires (T1-T2 assessment procedures) and interviews (during the T1- T2 assessment procedures and parental support intervention) are used. No biological sampling is carried out.

Participation in the study does not exclude the possibility of benefiting from traditional psycho-social care. During the study, if significant emotional distress is observed in one of the participants, appropriate management will be offered. In addition, if the child's caregiver with cancer dies during the study, participants will be able to benefit from specific care.

Concerning recruitment, the psychologists who suggest the intervention have been made aware of the study. The team of workers and interviewers is composed of psychologists and

doctors of psychology trained in the specific clinical aspects of psycho-oncology and family management.

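### Adjusting each planned analysis for the pre-randomisation T1 score would usually be more precise than comparing T1-to-T2 evolution, at almost no cost

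*Protocol*

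**What the plan says.** Section 3.5 (Statistical analysis) plans that a "mixed linear model including random effects will be used to compare the evolution of participants from the experimental condition to the control condition". It continues: "This analysis will be done separately for participants who performed the intervention individually and those who did it in dyads". The fixed effects are not listed. T1 is mentioned there only for control comparisons: the arms are compared at T1, and a further check is to "compare participants who performed T1 and T2 and those who dropped out (T1 completed").

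Section 3.1 sizes the trial on the same contrast: "The sample size was calculated a priori to detect differences in the evolution of the two groups", between T1 and T2. The effect size is introduced thus: "A pilot study suggests a minimum expected effect size of 0.8 (effect size) if the GC remains stable". With 5% significance and 90% power this gives 68 participants, 34 per group, and 80 are to be recruited to allow for dropout.

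Section 3.4 fixes the number of assessments: "This study includes 2 evaluation periods, T1 and T2". Section 3.2 fixes their order relative to allocation: "Randomization is done after the first evaluation so that evaluators and participants are not aware of the distribution at T1".

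**The concern.** With two waves, complete data and the usual arm, time and arm-by-time terms, the arm-by-time coefficient is simply the between-arm difference in mean change. That contrast subtracts the whole T1 score, which amounts to fixing the T2-on-T1 slope at 1. When the true slope is below 1, as is usual for questionnaire scores with moderate correlation over time, this adds noise. Because T1 precedes randomisation, estimating the slope instead introduces no bias.

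The protocol sizes a single comparison of 68, but section 3.5 runs the model separately by mode of participation. Each test of effectiveness therefore rests on only part of the sample, and that is where lost precision costs most. The T1 score is already collected from every participant, so the gain requires no extra recruitment.

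**Working it through.** **Inputs from the protocol.** Effect size 0.8, 5% significance, 90% power, 34 per arm (section 3.1); two assessments (3.4); T1 before randomisation (3.2); separate analyses (3.5).

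**Assumed, because the protocol does not give them.** The T1-T2 correlation r (0.3 to 0.9), the T2/T1 SD ratio, the individual/dyad split, the within-dyad correlation, and whether 0.8 is in change-score or raw-score SDs.

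**1. The plan's own figure.** A two-sided two-sample t test at 5% with d = 0.8 and 34 per arm has 90.2% power. The stated 68 reproduces.

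**2. The contrast.** In one simulated complete two-wave data set, the arm-by-time term of a random-intercept mixed model equalled the difference in mean change (0.8870 for both; SE 0.2006 for both).

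**3. Variance per participant.** Let s1 and s2 be the SDs at T1 and T2.

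- Change: s1² + s2² − 2·r·s1·s2
- T2 given T1: s2²(1 − r²)
- Difference: (s1 − r·s2)², never negative, and zero when the slope r·s2/s1 equals 1

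With equal SDs the ratio of adjusted to change variance is (1 − r²)/[2(1 − r)] = (1 + r)/2. Estimating the slope multiplies the adjusted variance by about 1 + 1/(N − 4), which is 1 + 1/30 = 1.0333 for N = 34. At r = 0.5 the ratio is 0.75 × 1.0333 = 0.775, a saving of 22.5%. Break-even is r = 2/1.0333 − 1 = 0.935.

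**4. Individual analysis, 17 independent participants per arm (68 split evenly), equal SDs.** Adjusted power uses 31 degrees of freedom.

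| r | Variance saved | Power, 0.8 in change SDs: change → adjusted | Power, 0.8 in raw SDs: change → adjusted |
|---|---|---|---|
| 0.3 | 32.8% | 61.9% → 78.7% | 48.1% → 64.4% |
| 0.5 | 22.5% | 61.9% → 72.8% | 61.9% → 72.8% |
| 0.7 | 12.2% | 61.9% → 67.4% | 83.1% → 87.5% |
| 0.9 | 1.8% | 61.9% → 62.6% | 99.9% → 99.9% |

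Simulation of the change-SD column (40,000 trials each) gave 78.8%, 72.8%, 67.3% and 62.6% for the adjusted analysis. In that column the implied raw effect is 0.8·√[2(1 − r)], so it falls from 0.95 SD at r = 0.3 to 0.36 SD at r = 0.9.

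**5. Unequal SDs, 17 per arm, slope cost included.** Variance saved:

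| T2/T1 SD ratio | r = 0.3 | r = 0.5 | r = 0.7 | r = 0.8 | r = 0.9 |
|---|---|---|---|---|---|
| 1.25 | 18.9% | 7.7% | −1.3% | −3.3% | 1.8% |
| 0.8 | 48.1% | 41.0% | 35.1% | 33.9% | 37.2% |

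At ratio 1.25 and r = 0.8 the slope is exactly 1.25 × 0.8 = 1. The 3.3% loss there is purely the cost of estimating it.

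**6. Dyad analysis, 8 dyads per arm, by simulation (20,000 trials each).** Own-T1 slope, dyad random intercept by REML, effect 0.8 in change SDs. The within-dyad correlation is the same at both times, and the cross-time partner correlation is r times it. Degrees of freedom are 14 for change and 13 for adjusted.

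| Within-dyad correlation | Change | Adjusted, r = 0.3 | r = 0.5 | r = 0.7 | r = 0.9 |
|---|---|---|---|---|---|
| 0.2 | 48–49% | 63.6% | 57.1% | 52.1% | 48.1% |
| 0.5 | 40–41% | 54.8% | 49.3% | 44.7% | 40.7% |

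At r = 0.9 there is effectively no gain in either row. A separate shorter simulation (6,000 trials each) gave adjusted power within about one percentage point of these figures.

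**The case against.** The strongest reply is that this is SAP material. The protocol does not list the fixed effects, and the arm-by-time specification is inferred. A mixed model that gives both arms a common T1 mean is also a mixed model comparing evolution, so section 3.5 as worded does not exclude the efficient analysis, and an SAP may already specify it. Sizing on a change contrast does not prevent adjustment at analysis.

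This stands in part. The planned analysis is not an error, and if an SAP already uses T1 in this way the gain has been taken and only the protocol wording needs aligning. But the protocol names evolution as the target in both the sample size and the analysis, and gives T1 no role in estimating the effect. The point therefore concerns a stated contrast as well as an omitted detail.

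A second reply is that the size of the benefit rests on assumptions and includes cells with no gain or a loss. That is correct, and those cells are shown above. The largest loss among the cases examined is 3.3% of variance, against savings of 12% to 33% for r from 0.3 to 0.7 with equal SDs.

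A third is that a T2 model adjusted for T1 drops participants who have T1 only, a group section 3.5 expects. That also stands, and it is a reason to choose explicitly between the two forms of adjustment.

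**Conclusion.** The point holds as a recommended improvement in precision. It shows no bias, no invalid test and no error in the sample size. It is conditional on the model having the usual arm-by-time terms. With equal SDs and 17 per arm, adjustment saves 12% to 33% of the variance for r between 0.7 and 0.3. That is worth roughly 4 to 17 percentage points of power across the two readings of the 0.8 effect size. The benefit is negligible near r = 0.9 and disappears where the T2-on-T1 slope is close to 1. The 17-per-arm and 8-dyad figures illustrate an unknown split. They should not be read as the trial's actual power.

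**What to change.** State in section 3.5 that, within each of the two planned analyses, the arm effect is the T2 difference adjusted for the participant's own T1 score, with a dyad random effect in the dyad analysis. A close alternative is a mixed model with a common T1 mean for both arms (time, and arm only at T2), which keeps the T1 data of participants without T2. The two are not identical when some participants have T1 only, or in dyads, so one should be named as primary.

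The cost is one sentence and about one degree of freedom per model, using data already collected. The sample size and the separate analyses by mode of participation stay as planned.

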There are currently only a few randomized studies evaluating the effectiveness of a psychological intervention to support parenthood that focuses on helping the child in an oncological context and that is offered to significant caregiver of the child. As part of a randomized and controlled study, a psychological intervention to support parenting was developed at the Jules Bordet Institute. This intervention is offered to significant caregivers of a child who have questions about the support a child needs when confronted with a parent's cancer. This intervention aims to develop and reinforce these supportive behaviors. The intervention is intended to be flexible (to respond to the medical situation), relatively brief (four sessions) and open to the heterogeneity of families (e.g., reconstituted, divorced, extended family). Significant caregiver of the child can participate either in pairs (in dyads) or individually.

2. Objectives of the study.

The intervention is evaluated in a randomized controlled study. To do this, two conditions are compared. The first condition ("control" condition) consists in the delivery of an information booklet entitled "How to talk with the child about a parental cancer? A practical booklet on communication. "[23] which contains parental information and recommendations associated with supporting a child facing a parent's cancer. The second condition ("experimental" condition) consists, in addition to providing the same information booklet, of a psychological intervention focused on supporting the child who has a parent with cancer.

2.1. Primary Objective.

The main objective of this study is to test the contribution and effectiveness of a psychological intervention in relation to the delivery of an informational booklet regarding participants' communication with the child in the oncology context. This intervention should increase participants' sense of communicative competence and communication behaviors.

2.2. Secondary objectives.

The information booklet should more specifically improve participants' knowledge of how to support a child facing a parent's cancer. Psychological intervention should have an impact not only on the sense of communicative skills but also on the emotional regulating capacity

associated with participants' communication with the child and on participants' concerns about the child. When the intervention is carried out in a dyad, it should also improve mutual support between participants.

3. Method

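### The 90% power is for one comparison of all 68 people, but effectiveness is tested separately in individual and dyad participants, and neither test has that power

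*Protocol*

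**What the plan says.** Section 3.1 states the purpose of the calculation: "The sample size was calculated a priori to detect differences in the evolution of the two groups", meaning control and experimental, between T1 and T2. With a minimum effect size of 0.8 taken from a pilot study and a control group that stays stable, "an overall population of 68 subjects (34 subjects in each group) will be required" for 5% significance and 90% power. Recruitment is raised to 80 to cover dropouts.

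Section 3.5 describes a linear mixed model with random effects that compares the evolution of the two conditions and so tests effectiveness. It continues: "This analysis will be done separately for participants who performed the intervention individually and those who did it in dyads". The section contains no efficacy analysis of the two formats together.

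Three other places bear on this:

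- Section 2.1 states the main objective without reference to format: to "test the contribution and effectiveness of a psychological intervention in relation to the delivery of an informational booklet".
- Section 3.2 describes how the format is chosen at recruitment: "As a first step, they are offered the opportunity to perform the dyad intervention". Individual participation is the fallback. No quota or expected mix is given.
- Section 3.3.2 treats the two formats as essentially one intervention: "The content does not change whether one is in a dyadic or individual intervention except that dyadic interactions and support are enhanced".

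**The concern.** The sample size and the analysis describe different tests. The calculation puts all 68 evaluable people into one comparison. The analysis divides them between two comparisons, in proportions that participants decide and the protocol does not fix. The stated power therefore belongs to a test that section 3.5 does not plan.

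At stake is the main objective. It concerns the intervention against the booklet as a whole, yet as written it is tested only in two smaller subsets. At an even split, each test would miss an effect of the planned size about 4 times in 10 instead of 1 in 10. The protocol also does not say what would be concluded if one test were significant and the other not. Estimating the effect by format is reasonable in itself; the fault is that the power claim does not apply to those tests.

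**Working it through.** **Inputs from section 3.1:** d = 0.8, 5% significance, 90% power, 34 per arm, 68 evaluable, 80 recruited.

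**Assumptions, because the protocol is silent:** two-sided test; 0.8 is the standardised difference in T1-T2 change, the same in both formats; 1:1 allocation within each format; people independent, except in step 4. With two time points, the arm-by-time term of a mixed model amounts to a comparison of changes, so the model adds no power over that comparison.

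**Formula.** For n per arm, power = P(|T| > t(0.975; 2n - 2)), where T is noncentral t with 2n - 2 degrees of freedom and noncentrality d x sqrt(n/2).

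**1. The protocol's own figure.** For n = 34 the noncentrality is 0.8 x sqrt(17) = 3.298 and the critical value is 1.997, giving power 0.9015. For n = 33, power is 0.8926. So 34 is the smallest n per arm that reaches 90%. A one-sided test would need only 28 per arm, so the figure is a two-sided one for a single test of all 68.

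**2. The separate tests at 68 evaluable.** For an even split, n = 17, the noncentrality is 0.8 x sqrt(8.5) = 2.332 and the critical value is 2.037, giving 0.619.

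| Split by format | n per arm (larger / smaller) | Power (larger / smaller) |
|---|---|---|
| 50/50 | 17 / 17 | 62% / 62% |
| 70/30 | 23.8 / 10.2 | 77% / 40% |
| 90/10 | 30.6 / 3.4 | 87% / 14% |

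Because 33 per arm already falls short, no split with people in both formats gives 90% in either test. The smaller format can never exceed 62%. At an even split, 90% power would require a true effect of about 1.15.

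**3. If all 80 were retained.** An even split (20 per arm) gives 69% in each test. One test reaches 90% only if at least 68/80 = 85% choose the same format; the other then has 24%. At 90/10 (36 and 4 per arm) power is 92% and 16%.

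**4. Correlation within dyads.** Assume both members are in the same arm and their changes have correlation ICC. The effective n per arm is then n/(1 + share in dyads x ICC).

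| Assumed ICC | Dyad test, even split of 68: 17/(1 + ICC) | Pooled test of 68, half in dyads | Pooled test of 68, all in dyads |
|---|---|---|---|
| 0.1 | 58% | 89% | 87% |
| 0.3 | 50% | 86% | 81% |
| 0.5 | 44% | 83% | 75% |

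Taking degrees of freedom from the number of dyads lowers the dyad test slightly further, to about 55%, 48% and 43%.

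In a simulation of change scores (40,000 runs, ICC 0.3), a pooled test that ignored the correlation had a type I error of 6.9% with about half the people in dyads and 8.9% with all in dyads. With the correlation modelled it was 5.1% in both.

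**5. Sensitivity to the meaning of 0.8.** Section 3.1 does not say what 0.8 is standardised by. Suppose it is the raw-score SD, with T1-T2 correlation r.

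- *Baseline-adjusted comparison*, d = 0.8/sqrt(1 - r²): at an even split, 74% for r = 0.5 and 89% for r = 0.7; at 70/30 with r = 0.7, 97% and 67%.
- *Comparison of changes*, d = 0.8/sqrt(2(1 - r)): at an even split, 48%, 62% and 83% for r = 0.3, 0.5 and 0.7; at 70/30 with r = 0.7, 94% and 60%.

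**6. Sizing each format.** For 90% in each test, 2 x 68 = 136 evaluable people are needed. At the protocol's own ratio that is 136 x 80/68 = 160 recruited, before any allowance for dyads.

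**The case against.** There are four serious points on the other side.

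**The percentages depend on how 0.8 is read.** If it is a raw-score effect and T1 and T2 are strongly correlated, the larger format can pass 90%. This is true and is shown in step 5. But only an effect of 0.8 on the tested contrast reproduces 34 per arm at 90%, and section 3.1 speaks of differences in evolution. Even on the favourable reading, the smaller test at 70/30 has at most 67%.

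**Missing 4 in 10 is a figure per test.** With independent people and the same effect in both formats, the chance that at least one test is significant is 1 - (1 - 0.619)² = 85% at an even split, 86% at 70/30 and 89% at 90/10. That is fair, but it is still below 90%. It also carries a chance of 1 - 0.95² = 9.75% of at least one false positive. Both tests succeed only 0.619² = 38% of the time at an even split, and no rule for combining them is stated.

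**The loss depends on an unknown mix.** Since the dyad is offered first, the split could be lopsided, and at 90/10 the larger test has 87%. That limits the loss for one format only; the other has 14%. The mismatch costs power and precision, and does not bias the estimates.

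**A statistical analysis plan may add a pooled analysis.** The protocol does not leave the matter open: it specifies separate analyses and claims 90%. A pooled primary analysis elsewhere would still have to be reconciled with section 3.5. The structure of the random effects, by contrast, may properly be left to that plan.

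**Conclusion.** The concern holds. The 90% in section 3.1 describes one test of all 68 people, and section 3.5 plans two tests of parts of them. If 0.8 is the standardised difference in change and people are independent, neither test reaches 90% at 68 once both formats are used, whatever the mix. The size of the shortfall depends on the mix: 62% each at 50/50, and from 77% and 40% to 87% and 14% as the split moves from 70/30 to 90/10.

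The mismatch itself is certain from the text. The exact percentages rest on the reading of 0.8 and on an equal effect in both formats. The dyad figures rest further on assumed correlations that the protocol does not supply. Because this concerns the main efficacy test and its stated power, it should be corrected before analysis.

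**What to change.** **Section 3.5.** Make the primary efficacy analysis one mixed model on all randomised participants, by randomised arm, with time, arm x time and the format declared at T0. Include a random effect that lets the T1-T2 change correlate within a dyad, such as dyad-by-time, or use errors clustered by dyad. Random intercepts alone are not enough, because with two time points they cancel from the change. Report the format-specific analyses as secondary, through an arm x time x format interaction with an estimate and confidence interval for each format.

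**Section 3.1.** State what 0.8 is standardised by. Restate the pooled power at 68 as about 90% if changes are independent, about 86% with half the people in dyads and about 81% with all in dyads, naming the assumed correlation of 0.3 and showing a range around it.

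**If the separate analyses are to stay primary.** Either delete the 90% claim and give the power of each test over the plausible range of splits, or size each format (136 evaluable, about 160 recruited, before allowing for dyads). State how two differing results would be read.

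**Cost.** The pooled route needs only wording in two sections. Its downsides are that the primary estimate averages over the two formats, and that the honest power at 68 is somewhat below 90%. Holding 90% with everyone in dyads at a correlation of 0.3 would need about 68 x 1.3 = 88 evaluable people. Which analysis is primary is for the trial team to decide; the power statement has to match the choice.

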After receiving the information booklet, randomized participants in the control condition are placed on a waiting list. Nine weeks after the end of T1, these participants have a second evaluation time (T2) consisting of the completion of questionnaires and a semi-directive interview. They subsequently benefit from parental support intervention.

The entire study was manualized and standardized in order to best meet the methodological recommendations recommended by "CONSORT"[18].

Information booklet: "How to talk to your child about a parental cancer? A practical booklet on communication. » [23]

All participants (control and experimental conditions) receive an information booklet containing parental information and recommendations associated with supporting a child facing a parent's cancer. To address this theme, the booklet describes concepts related to child

development such as understanding the disease, reactions and needs. It also presents recommendations related to communication around the disease according to the child's age and development (*what to say to the child?* and *how to respond to the child?*). Finally, the booklet offers resources (e.g., books, websites, non-profit organisations) that are useful in this context.

3.3. Parental Support Intervention.

3.3.1. Objectives of the intervention.

While the information booklet mainly aims to increase the knowledge of significant caregivers about supporting a child facing a parent's cancer, the parental support intervention aims to develop and reinforce their behaviors associated with supporting the child in this context. The intervention aims to improve communication with the child by strengthening the sense of communicative competence and transmitting emotional regulation strategies. The dyad intervention also aims to strengthen mutual support between participants.

3.3.2. Content of the intervention.

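### T2 in the experimental arm depends on finishing the intervention while control T2 does not, and the wording of the two analysis sets permits a performers-only reading

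*Protocol*

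**What the plan says.** Protocol Section 3.2 fixes the order of events. Format is settled first, at recruitment (T0): "As a first step, they are offered the opportunity to perform the dyad intervention". The fallback is also settled there: "If this is not possible, participants have the opportunity to participate in an individual way". Consent is next: "After this step of presenting the information, they sign a consent form for inclusion in the study". T1 then takes place with the format already in place: "As soon as they are included, the participants (in dyads or individually) have a first evaluation time (T1"). Allocation comes last: "Randomization is done after the first evaluation so that evaluators and participants are not aware of the distribution at T1".

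The same section schedules T2 by two different rules. For the experimental arm: "Fifteen days after the end of the intervention, these participants have a second evaluation (T2"). For the control arm, T2 falls nine weeks after T1 ends, whatever has happened in between. Of the controls it then says "They subsequently benefit from parental support intervention", so no control has had a session when the outcome is measured.

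Section 3.5 plans a mixed linear model that compares change between the two conditions, and continues: "This analysis will be done separately for participants who performed the intervention individually and those who did it in dyads". It also plans to compare participants with both assessments against those who dropped out after T1.

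**The concern.** A randomised comparison needs the outcome to be sought from everyone allocated, by a rule that does not depend on what happened to them after allocation. Here the rule for one arm depends on a post-allocation event, the end of the intervention, and the rule for the other arm does not. A caregiver allocated to the sessions who never attends, or who gives up after one or two, may simply never be invited to T2. A control in the same circumstances is invited at nine weeks.

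The protocol foresees such cases. Section 3.1 allows for dropouts, and Section 4 lets participants leave at any time and considers a death in the family during the study. Caregivers who stop the sessions may well differ in how they communicate with the child. If they do, the experimental T2 scores come from a selected group and the control scores do not.

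The Section 3.5 wording could compound this. An analyst who takes it at face value could leave out experimental participants who did not carry out the sessions while keeping every control.

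**Working it through.** **Step 1: is T2 defined for every allocated participant?** Applying the Section 3.2 rules case by case:

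| Participant | T2 under the written rule |
|---|---|
| Control, any | Nine weeks after T1 ends |
| Experimental, all four sessions attended | 15 days after the last session |
| Experimental, stops early | Unclear: the end could be the last session attended or the planned fourth session |
| Experimental, never starts | None: there is no end to count from |

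The last two rows have no counterpart in the control arm. This gap is in the visit schedule, and no later analysis can supply assessments that were never arranged.

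**Step 2: are the two analysis sets formed after randomisation?** The sequence in Section 3.2 is format, consent, T1, randomisation. Section 3.4 agrees: dyads complete two additional questionnaires and settle on the reference child together, so format is known at T1 in both arms. Format is therefore a baseline variable. Section 3.5, however, names the sets by how the intervention was performed. By T2 no control has performed it, so controls can be sorted only by planned format. The text does not say that experimental participants are to be sorted in the same way.

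**Step 3: what do the plan's own figures say about loss?** Section 3.1 gives 34 per group for a standardised effect of 0.8 at 5% and 90% power. A two-sided two-sample t-test gives 33.8, so 34 per group and 68 in all, as stated. The recruitment target of 80 implies an allowance of 1 − 68/80 = 0.15. That allowance covers both arms together and does not separate stopping the sessions from leaving the study. The protocol gives no adherence rate.

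**Step 4: how large could the bias be?** The documents do not fix this, so the values here are assumed. Let a fraction f of the experimental arm have no T2, let all controls have one, and let the tendency to stay have correlation r with the outcome (both standard normal, lowest f lost). The experimental mean, and so the difference between arms, shifts by

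r × φ(z) / (1 − f), where z is the f quantile and φ the standard normal density.

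- f = 0.10, φ = 0.1755: r = 0.3 gives 0.3 × 0.1755 / 0.90 ≈ 0.06 SD; r = 0.5 gives ≈ 0.10 SD.
- f = 0.15, φ = 0.2332: r = 0.3 gives 0.3 × 0.2332 / 0.85 ≈ 0.08 SD; r = 0.5 gives ≈ 0.14 SD.
- f = 0.20, φ = 0.2800: r = 0.5 gives 0.5 × 0.2800 / 0.80 = 0.175, about 0.18 SD.
- r = 0: no shift for any f.
- r negative: the same sizes with the sign reversed.

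A mixed model that keeps participants with T1 only can remove the part of this that T1 scores explain. In that case r should be read as the association that remains after T1.

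**The case against.** The strongest reply is that Section 3.5 uses a loose label and states no exclusion. Format is fixed before allocation. No minimum attendance and no completers' set are stated. Read strictly, the sentence would leave no controls in either set at T2, so the planned comparison could not be run. Analysis populations and missing-data handling may be in an analysis plan that is not shown, and a mixed model need not discard a participant who lacks T2.

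Most of this stands. A reader might infer that the sets are formed by a post-randomisation event and that the effect is therefore overstated. The documents do not support either inference: the T0 format is the most coherent reading, and nothing shows who would stop or in which direction their scores would differ.

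A reader might also scale the 0.8 effect down by the 15% allowance and call the gap the bias. That is not supported either. The allowance is for both arms and is not a rate of non-attendance. Zero gain in those lost is an assumption. The protocol does not say whether the pilot effect refers to completers. And the gap would measure dilution of the effect, not selection.

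Two things are not answered. The T2 rule is a design rule in the protocol, and it leaves early stoppers without a clear date and non-starters without any T2, however the Section 3.5 sentence is read. And the same paragraph of Section 3.5 uses the same verb for participants who actually completed both assessments, as against those who dropped out, so a literal reading of the sentence is a natural slip.

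**Conclusion.** The point holds as a gap in outcome collection with a related wording weakness. As written, T2 depends on adherence in the experimental arm and not in the control arm. This may bias the comparison, with direction and size depending on who stops. The documents allow no estimate; the 0.06 to 0.18 SD in the illustration rests entirely on assumed loss and correlation, and the shift is zero if stopping is unrelated to outcome. The conclusion assumes that the visit rule is followed literally. If staff in practice invite everyone to T2, the gap is only in the text. The planned comparison of dropouts with completers would describe the loss but would not recover the missing outcomes.

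**What to change.** 1. In Section 3.2, add that experimental participants who do not start or do not finish the sessions are invited to T2 nine weeks after T1 ends, the point already used for controls. Participants who finish keep the present rule.
2. In Section 3.5, define the two sets by the format (individual or dyad) recorded at T0 before randomisation, and state that all randomised participants are analysed in their assigned arm and T0 format, whatever number of sessions they attended. A dyad that loses a member then stays in the dyad set.

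The cost is two wording changes and a few more T2 assessments, each with a research interview of about an hour and a half according to Section 3.4. The reported effect may be somewhat smaller, because participants who had little or none of the intervention then count in the experimental arm.
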